# 4. **STUDY DESIGN**

## 4.1 **Overall Design**

This is an exploratory Phase 1, blinded, randomized, dose-finding influenza virus challenge study in approximately between 62-114 (targeted maximum sample size of 106 active plus 8 shams) males and non-pregnant females, 18 to 45 years old, inclusive, who are in good health and meet all eligibility criteria. The clinical study is designed to determine the optimal infectious dose and safety profile of a recombinant influenza A/Texas/71/2017 (H3N2) clade 3C3a strain in healthy adult volunteers.

The study will enroll approximately between 13-39 subjects in each of up to 3 challenge dose groups at 2 sites (Duke University [DU] and University of Maryland [UMD]) for approximately between 62-114 subjects total for the study. We plan to enroll each challenge dose group according to an adaptive dose-escalation schedule (Figure 1) which allows study results (see Section 9.5.6) to be analyzed between challenge cohorts to inform the sample size and virus dose for the next escalation cohort(s). The study timeline anticipates 4-6 weeks of lead-time for studyspecific screening and start-up activities for the initial cohort, and similarly, 4-6 weeks between subsequent cohorts at each site to evaluate study results and turn-over of the clinical unit. However, to compress the overall dosing timelines, challenge cohorts may be performed concurrently or around a 2-week timeline between the sites. We plan up to 2 weeks (Day -2 to Day 8) to complete the clinical in-patient component for each challenge cohort, thus altogether projecting the following to complete the dose-ranging clinical confinement component: up to 3.5 to 4 months, if 3 challenge cohorts evaluated; 4 to 4.5 months, if 4 challenge cohorts evaluated; 5 to 6 months if 5 challenge cohorts evaluated; and 5.5 to 6.5 months if 6 challenge cohorts evaluated. Each participant has an additional 7 weeks of follow-up post confinement. The study period could range from approximately 7.5 months to one year, depending upon the number of challenge cohorts enrolled.

Potentially eligible study subjects may be pre-screened under an active screening protocol (DMID 20-0004) to identify those with HAI antibody titers  $\leq$ 1:40 specific to the challenge virus strain.

During the study screening period of this protocol (Day -45 to Day -3), participants who have not received a seasonal influenza vaccine within the past 4 months and for whom there are no safety concerns from standard safety assessments and screening labs, are eligible for enrollment to the study. Backup subjects will be confined under respiratory isolation prior to challenge to ensure sufficient number of volunteers undergo challenge, given the potential for dropouts, development of exclusion criterion, and/or pre-challenge evidence of viral respiratory infection among subjects. The number of backup subjects will depend on site-specific considerations, such as anticipated drop-out rates, anticipated development of new exclusionary criteria, and respiratory virus circulation in the community. Safety assessments and safety labs include a medical history review, physical examination, ECG, a chest X-ray (CXR), HIV and hepatitis B/C testing, baseline SpO2 saturation, and testing for WBCs, ALC, hemoglobin, platelets, ALT, and creatinine. Women of childbearing potential must have a negative serum pregnancy test at screening and a negative urine pregnancy test on Day -2. Likewise, participants (including

backup subjects) must have a negative drug urine toxicology test (unless the drug is deemed acceptable by the Investigator), negative multiplex respiratory viral test, and a negative SARS-CoV-2 RT-PCR test at screening and on Day -2. After a standard physical exam to exclude active infection or other illness, participants will begin confinement on Day -2 and remain confined for up to 12 days (Days -2 to 10). Backup subjects will also begin confinement on Day - 2 (either within the confinement facility or at an alternate location under respiratory isolation). They will be discharged prior to challenge if they are not needed. All backup subjects replacing discharged subjects will be admitted to the confinement unit prior to viral challenge and remain confined in the confinement unit through Day 10.

On Day 1, subjects will be randomized and administered a single challenge dose of either a sham inoculum or a virus dose between  $10^4$  and  $10^6$  TCID50. The challenge inoculum will be administered using the MAD NasalTM Intranasal Mucosal Atomization Device (Teleflex, Morrisville NC) attached to a 1cc syringe. Approximately 500 µL of study product will be delivered in each nostril with the subject in a recumbent position. Subjects, clinical study staff, administrators of challenge inoculum, and clinical evaluators will be blinded as to whether the participant received either sham or virus challenge inoculum. The dosing plan will follow an adaptive dose-escalation schedule (Figure 1) that will include up to 8 different challenge cohorts. This dosing plan is designed to optimize subject safety, starting with a low dose and allowing flexibility to make informed adjustments between challenge cohorts from outcome results of the previous challenge cohort. For the first exposure in humans, the initial low dose challenge will be conducted in a group of a targeted total of 13 subjects (including 1 sham) to assure the virus is safe with no study-related or unanticipated adverse events observed or reported before further use. Dose escalation to the next (higher) dose and subsequent higher doses, if necessary, will be informed by both safety and AR outcomes given a pre-specified decision algorithm (see section 9.3.2) for dose-escalating.

Clinical outcomes and pre-defined halting criteria will be used to determine whether the trial moves forward to the higher dose of the challenge strain.

## **Clinical Outcomes**

Symptomatic influenza virus infection criteria will be based on the virologic assessment and the modified Jackson score. A subject will be defined as having symptomatic influenza virus infection if the following criteria are met:

- Viral shedding detected in NP swab(s) by qualitative RT-PCR on at least two days beginning 24 hours after challenge until Study Day 8.
- A cumulative symptom score ≥ 6 from daily component symptoms, including documented fever, computed across any consecutive 5-day window through Day 8 beginning on Day 2 post challenge using a modified Jackson score. Highest point score per day per sign or symptom will be used. Component signs and symptoms include fever, lymphopenia (< 1000 cells/mL), runny nose, stuffy nose, sneezing, sore throat, headache, cough, malaise, body ache, chills, feverish, shortness of breath, and earache ranked on a 4-point severity scale (0-3). (Appendix A for Temperature). Temperature will be measured three times a day and symptoms will be collected twice daily on the modified Jackson score.

# *Note: A documented fever and feeling feverish will count as one point on the cumulative symptom score.*

Signs and symptoms will also be collected via the FLU-PRO and Validation Diary instrument which will be completed once daily after 3:00 pm through confinement. Subjects will continue to complete the FLU-PRO daily after discharge through Day 15. The modified Jackson score and FLU-PRO will be compared in exploratory analyses.

• Component signs and symptoms of the FLU-PRO and Validation Diary include runny/dripping nose, congested/stuffy nose, sinus pressure, scratchy or itchy throat, sore or painful throat, difficulty swallowing, teary or watery eyes, sore or painful eyes, eye sensitivity, trouble breathing, chest congestion, chest tightness, dry or hacking cough, wet or loose cough, nausea, stomach ache, dizziness, head congestion, headache, lack of appetite, excessive sleepiness, body aches or pains, weakness or tiredness, chills or shivering, feeling cold, feeling hot, and sweating.

### Safety Threshold

The safety threshold is defined as meeting one of the protocol-defined halting criteria outlined in Section 7.1.1 which includes the occurrence of severe influenza complications in any study subject (Section 2.3.1). If a subject has a severe influenza complication(s), the study staff and subject will be unblinded as to receipt of challenge virus or sham and as to the results of influenza RT-PCR testing for safety evaluation and potential therapeutic intervention with an approved influenza antiviral agent.

In this adaptive schema, the initial cohort (Cohort 1A) for the lowest challenge dose group will include a targeted total of 12 subjects receiving 10^4 TCID50 of the challenge strain and one subject receiving sham placebo. If fewer than 80% of subjects meet the case definition for influenza in Cohort 1A, the dose will escalate to 10^5 TCID50 to include Cohort 2A. If 80% or more subjects in Cohort 1A meet the case definition for influenza, the lowest challenge dose group will be expanded to include a targeted total of 12 additional subjects receiving 10^4 TCID50 of the challenge strain and one subject receiving sham placebo to comprise Cohort 1B. Cumulatively, if fewer than 80% of subjects in Cohorts 1A and 1B meet the case definition for influenza, the dose will escalate to 10^5 TCID50 to include Cohort 2A. If 80% or more of the subjects in Cohorts 1A and 1B meet the case definition for influenza than the lowest challenge dose group will be expanded to include a targeted total of 12 additional subjects receiving 10^4 TCID50 of the challenge strain and one subject receiving sham placebo to comprise Cohort 1C. Cumulatively, if fewer than 80% of subjects in Cohorts 1A, 1B, and 1C meet the case definition for influenza the dose will escalate to 10^5 TCID50 to include Cohort 2A. If 80% or more of the subjects in Cohorts 1A, 1B, and 1C combined meet the case definition for influenza then the optimal dose of 10^4 TCID50 will be selected.

The  $10^5$  TCID50 challenge dose group similarly includes up to three cohorts each with a targeted total of 12 subjects receiving  $10^5$  TCID50 of the challenge strain and one subject receiving sham placebo with the thresholds for dose escalation to  $10^6$  TCID50 being < 70% subjects for Cohorts 2A, 2B, and 2C cumulatively moving from Cohort 2A to Cohort 2B and Cohort 2C, respectively. The highest challenge dose group to be evaluated in this study is  $10^6$ 

Protocol 20-0005	Version 8.0
H3N2 Dose-Ranging Challenge	04May2023

TCID50, with each of two challenge cohorts including a targeted total of 17 subjects receiving  $10^6$  TCID50 of the challenge strain and one subject receiving sham placebo.

Following virus challenge, subjects will be monitored daily for up to 7 days post-challenge (Days 2-8). During this confinement period, time-series collections of biological samples and clinical information will occur daily from pre-challenge (baseline) through Study Day 8. The different specimen types and clinical assessments are shown in (Table 1). Whole blood samples will be processed into component parts (e.g., PBMCs, plasma, sera, RNA, DNA) to evaluate multiple host response systems including the immune, molecular, and cellular responses in the circulation and nasal mucosa. Additionally, subjects will be provided wearable devices for continuous monitoring of physiological measures including heart rate, ECG, body temperature, and sleep habits.

Examples of the devices used in the study include those listed below. Other devices approved for consumer and/or clinical use may also be used, provided they are fully non-invasive and do not present any additional risk to study subjects:

• Garmin Vivosmart 4: This commercially available product is intended for training and recreational use. It is worn on the wrist and uses photoplethysmography (PPG) technology along with mechanical sensors to measure heart rate, oxygen saturation, activity, etc. The Garmin will transfer the subject's data via Bluetooth to the smartphone where the compatible app has been installed. These apps will then upload the data to cloud-based servers maintained by the individual device manufacturers. Data will then be uploaded to a secure server at the study sites.

• Oura Ring: This commercially available product is intended for training and recreational use. It is worn on the finger and uses photoplethysmography (PPG) technology along with mechanical sensors to measure heart rate, body temperature, activity, etc. The Oura Ring will transfer the subject's data via Bluetooth to the smartphone where the compatible app has been installed. These apps will then upload the data to cloud-based servers maintained by the individual device manufacturers. Data will then be uploaded to a secure server at the study sites.

• Bittium Faros 180: This FDA approved and CE marked medical device is available for clinical use; specifically for outpatient monitoring or occupational therapy after a cardiac event. It has an ECG sensor and accelerometer and can be worn using cable/electrode connections, or over the chest with a fabric strap. Data collected by the Faros 180 will be manually uploaded (via USB) to a secure cloud server maintained by the sites.

For safety assessments, ECG, and safety lab results will be evaluated at pre-specified timepoints as well as daily targeted physical exams during confinement. Viral shedding will be measured by quantitative RT-PCR and culture, as well as qualitative multiplex RT-PCR tests using the BioFire or Luminex respiratory viral panel performed daily on nasal swab(s). In parallel to specimen collections, subjects will provide self-reported symptom diaries once daily through Study Day 15 using a standard symptom instrument, FLU-PRO and Validation Diary. The modified Jackson score will be administered by study investigators twice daily through confinement and once at the Study Day 15 visit. On Study Day 8, subjects may be discharged once they meet all of the following discharge criteria (subjects meeting discharge criteria may leave after receipt of qualitative RT-PCR results for the day):

• Have two qualitative RT-PCR tests on NP swabs (that are collected 12 hours apart on Study Day 6 or thereafter on consecutive days) that are negative for influenza A using a multiplex respiratory virus assay (BIOFIRE® FILMARRAY® respiratory panel by bioMérieux or Luminex xTAG®).

- Are afebrile (< 100.6°F/38.1°C).
- $SpO_2 \ge 95\%$  on room air
- Show no signs or symptoms of moderate or severe influenza (Section 2.3.1) by clinical evaluation.
- Are clinically and hemodynamically stable for at least 48 hours (per the evaluation of the licensed study clinician listed on the Form FDA 1572).
- All AEs and SAEs will be recorded on the appropriate DCF.

Subjects and study staff performing clinical evaluations and assessments will remain blinded to results of RT-PCR testing for influenza only until Study Day 6 or upon early discharge. The study team will not be blinded to RT-PCR testing for other respiratory pathogens. Subjects will be offered a course of an antiviral (oseltamivir or baloxavir marboxil) if they remain symptomatic and/or have a positive influenza test by qualitative RT-PCR on Study Day 6. Treatment can begin as early as Study Day 6 after test results are received. Subjects will remain in confinement until they have two negative influenza tests by qualitative RT-PCR. The two tests must be collected at least 12 hours apart. Subjects will return for three follow-up visits at approximately Days 15, 29 and 57 post-challenge to assess overall health and for additional specimen and clinical data collections.

Schedule of assessments can be found in Section 1.2, Schedule of Activities Protocol Schema can be found in Section 1.3, Study Schema. Dose escalation or dose-ranging details are found in Section 6.1.2, Dose Escalation Full details of interim analysis are found in Section 9.5.6, Planned Interim and Early Analyses

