### Safety

Between each challenge cohort, an Internal Safety Review Committee (ISRC) will review blinded subject data from Days 1 through Day 8 to assess if any of the halting criteria (Section 7.1.1), including the occurrence of serious and severe influenza illness (Section 2.3.1), is met. If none of the halting criteria is met, as assessed by the ISRC, the study can proceed to enroll the next challenge cohort according to the adaptive trial design. If any of the halting criteria are met, an SMC will review the subject safety data in an ad hoc meeting.

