## 4.3 Justification for Dose

Protocol 20-0005	Version 8.0
H3N2 Dose-Ranging Challenge	04May2023

Subjects will be randomized and administered a single challenge dose of either sham placebo or a virus dose between  $10^4$  to  $10^6$  TCID50. Historically, a  $10^4$  TCID50 has been safely used as the lowest dose tested in challenge studies[5-7]. There is no indication from non-clinical studies of the recombinant influenza A/Texas/71/2017 (H3N2), clade 3C3a virus in mouse, hamster and ferret models of infection that this virus will behave any differently in humans than the wild-type parent influenza virus.

The dosing plan will follow an adaptive dose escalation schedule (**Figure 1**) that will include up to three different challenge dosing groups. This dosing plan is designed to optimize subject safety, starting with a low dose and allowing flexibility to make informed adjustments between challenge cohorts from outcome results of the previous challenge cohort. The plan is guided by our experience and the results of our 3 previous human titration studies.

For the first exposure in humans, the initial low dose challenge will be conducted in a group of a targeted total of 12 subjects (and 1 sham) to assure the virus is safe with no study-related or unanticipated adverse events observed or reported. Dose escalation to the next dose level and subsequent higher doses, if necessary, will be informed by both safety and AR outcomes given a pre-specified decision algorithm for dose-escalating. The decision to escalate or not escalate to the next challenge dose will involve the following criteria:

- The tested dose is determined to be safe with no occurrence of halting criteria or severe influenza complications
- An AR < 80% triggers dose escalation in the 10^4 TCID50 challenge dose group.
- An AR < 70% triggers dose escalation in the  $10^5$  TCID50 challenge dose group.
- An AR  $\ge$  80% in the 10^4 TCID50 challenge dose group would stop escalation, and a repeat of the presumed optimal dose for up to 3 total challenge cohorts: 1A, 1B and 1C.
- An AR  $\geq$  70% in the 10^5 TCID50 challenge dose group would stop escalation, and a repeat of the presumed optimal dose for up to 3 total challenge cohorts: 2A, 2B and 2C.

NOTE: AR is the percentage of participants meeting the pre-defined symptomatic influenza infection definition described in section 4.1.

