## 7. STUDY INTERVENTION DISCONTINUATION AND PARTICIPANT DISCONTINUATION/WITHDRAWAL

## 7.1 Halting Criteria and Discontinuation of Study Intervention

#### 7.1.1 Study Halting Criteria

Additional enrollment and interventions/administration of study products will be paused for Safety Monitoring Committee (SMC) review/recommendation if any of the following events are reported:

- 1. Any subject experiences laryngospasm, bronchospasm, or anaphylaxis within one day after challenge.
- 2. Two or more subjects experience generalized urticaria (defined as occurring at more than two body parts) within three days after challenge.
- 3. Any subject experiences a related SAE during the confinement unit period.
  - This includes any subject who develops a severe influenza complication (Section 2.3.1) during the confinement unit period and requires admission to an Intensive Care Unit (ICU), and/or receipt of ICU level of care
- 4. Two or more subjects per challenge cohort (or four or more subjects per dosing group) experience the same related grade 3 AE of any kind after challenge through the confinement unit period and related to study product.
- 5. Any medically significant safety issue that the PI determines should halt the study.

The SMC is external to the DMID and comprises at least 3 voting members. The SMC will consist of members with appropriate expertise to contribute to the interpretation of the data from this study. Its activities will be delineated in a SMC charter that will describe the membership, responsibilities, and the scope and frequency of data reviews. The SMC will operate on a conflict-free basis independently of the study team. The DMID or the SMC may convene ad hoc meetings of the SMC according to protocol criteria or if there are concerns that arise during the study.

As defined in the charter, the SMC will review data at specified times during the course of the study for subject and overall study progress and will conduct ad hoc reviews as appropriate when a halting rule is met or for immediate concerns regarding observations during this study. The SMC will hold the following meetings; an organizational meeting prior to subject enrollment, any ad hoc meetings when a halting rule is met or due to specific safety issues as the SMC deems necessary, and a final meeting to review cumulative safety data.

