## 9.5.6.2 Interim Review to Determine the Dose for the Subsequent Cohort

After all subjects from each challenge cohort have been discharged from the challenge unit, the infection, symptom, and safety data will be cleaned to prepare for the interim review to determine the dose for the next challenge cohort enrolled.

If the minimum symptomatic influenza AR threshold given in **Figure 1** is met and no halting criteria for safety have been met, the next group of subjects will be enrolled at the same dose level. If the threshold is not met and no halting criteria have been met, the next cohort will be enrolled at the next highest dose level. If the halting criteria are met, the SMC will review to determine whether the study should be halted due to safety concerns.

Data will be considered in aggregate as part of the interim reviews for dose selection, in order to minimize the potential for unblinding.

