The study design is presented in [Figure 1](#). The AR is measured as the proportion of participants meeting the criteria for symptomatic influenza infection described above (and in [Section 3.2](#)), and the safety threshold used to halt dose escalation is given by the halting rules described in Section 7.1.1 of the protocol. Note that the AR was determined across all participants in a challenge cohort, blinded to receipt of active challenge virus or sham inoculum.

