4.6.2. Safety Variables

Safety is assessed by the incidence, frequency, and severity of:

1. Study product-related serious adverse events occurring from the time of the challenge through the end of the study (approximately 2 months post-challenge).
2. Clinical safety laboratory adverse events occurring from the time of challenge through Study Day 8. Parameters to be evaluated include: white blood cells (WBCs), absolute lymphocyte count, hemoglobin, platelets, and alanine transaminase (ALT), and creatinine (Cr).
3. Adverse Events (AEs) – non-serious adverse events occurring from the time of challenge through approximately 28 days post-challenge.

Unsolicited Adverse Events

The FDA defines an AE as any untoward medical occurrence associated with the use of a drug in humans, whether or not considered drug related (21 CFR 312.32 (a)). An AE can therefore be any unfavorable and unintended sign (including an abnormal laboratory finding), symptom, or disease temporally associated with the use of medicinal (investigational) product.

In this study, solicited symptoms of symptomatic influenza infection are collected from the time of challenge through 7 days post-challenge and will not be considered adverse events. Objective clinical examination findings consistent with the solicited symptom, such as oropharyngeal erythema or lymphadenopathy, will also not be considered AEs. Any influenza signs, symptoms or lab findings determined by the clinician to have exceeded the expected severity or any moderate or severe complications, as listed in Section 2.3.1 of the protocol, are considered unsolicited adverse events. Events that are not consistent with illness due to influenza, and events that occur after administration of antivirals, are considered unsolicited AEs as well. Note that there are no solicited AEs for this study.

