10.2. Deaths, Serious Adverse Events and other Significant Adverse Events

A listing of serious adverse events (SAEs), including any deaths reported during the study, will be presented in [Table 61](#). Severe influenza complications reported as adverse events will be reported in [Table 62](#).

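### Protocol 4.1 and 4.3 make a severe influenza complication in any subject a safety stop for dose escalation, but the halting criteria in 7.1.1 contain no such item

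*Protocol*

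**What the plan says.** Five places in the two documents describe the safety condition for moving to a higher dose.

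- **Protocol 4.1, Safety Threshold.** The threshold is a met criterion from 7.1.1, "which includes the occurrence of severe influenza complications in any study subject". The text refers to the list in 2.3.1 and sets no limit by seriousness, relatedness or timing.
- **Protocol 1.1, Safety.** The ISRC checks the 7.1.1 criteria on Day 1 to Day 8 data, "including the occurrence of serious and severe influenza illness (Section 2.3.1), is met".
- **Protocol 4.3.** The first listed criterion for the escalation decision is: "The tested dose is determined to be safe with no occurrence of halting criteria or severe influenza complications". Severe complications stand beside the halting criteria as a separate condition.
- **Protocol 7.1.1.** Severe complications appear once, under item 3 (a related SAE during confinement), as an included example: "any subject who develops a severe influenza complication (Section 2.3.1) during the confinement unit period and requires admission to an Intensive Care Unit" or ICU-level care.
- **Protocol 9.5.6.2 and SAP 4.1.** The protocol says: "If the threshold is not met and no halting criteria have been met, the next cohort will be enrolled at the next highest dose level". The SAP says that "the safety threshold used to halt dose escalation is given by the halting rules described in Section 7.1.1 of the protocol".

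**The concern.** Section 4.1 credits 7.1.1 with a rule that 7.1.1 does not contain. A reader who starts from 4.1 or 4.3 expects one severe complication in any subject to hold escalation. A reader who follows 7.1.1 and 9.5.6.2 may find no criterion met and enroll the next cohort at ten times the live-virus dose. This is the first human exposure to this challenge virus, so whether a single severe complication pauses dosing should not depend on which section is open, or on whether someone chooses to use discretion.

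**Working it through.** No arithmetic underlies the point. The check is to run single cases through each rule.

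**What 7.1.1 catches from one subject.** Item 1 covers airway spasm or anaphylaxis within a day of challenge. Item 2 needs at least two subjects with generalized urticaria. Item 3 needs an SAE that is related and occurs in confinement. Item 4 needs the same related grade 3 AE in at least two subjects of a cohort, or four of a dose group, within confinement. Item 5 is the PI's judgment. One event can therefore trigger an automatic pause only through item 1 or item 3.

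**Is a severe complication always an SAE?** Not by rule. Protocol 8.3.1 and SAP 4.6.2 record them as AEs; in the SAP's words, "any moderate or severe complications, as listed in Section 2.3.1 of the protocol, are considered unsolicited adverse events". Seriousness is a separate test in 8.3.2, based on outcome or on medical judgment. Section 2.3.1 lists 14 severe complications. Death and hospital admission are serious by definition, and several others would usually be judged serious. Severe bronchitis and Bell's palsy are examples that might not be.

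**Single cases, taking the attack rate to be below the escalation threshold:**

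| One severe complication | 4.1 and 4.3 | 7.1.1 automatic items | 9.5.6.2 |
|---|---|---|---|
| Related, serious, in confinement | Hold | Item 3 met | SMC review |
| Related, judged non-serious, in confinement (not an item 1 event) | Hold | None met | Next dose |
| Related, serious, first arising after discharge | Hold | None met | Next dose |
| Related, non-serious, first arising after discharge | Hold | None met | Next dose |

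The sections disagree in the last three rows. Serious events after discharge do reach the sponsor (8.3.5.1) and the SMC (8.3.2), but neither section says that escalation waits for their review.

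**Is there time for a post-discharge event to matter?** Discharge can occur from Day 8. AEs are collected for 28 days after challenge, to Day 29, which leaves 29 − 8 = 21 days of collection after the earliest discharge. The dose decision follows discharge of the whole cohort and data cleaning (9.5.6.2), so some of that window precedes it. How much is not stated.

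**Where it can arise.** An escalation decision can follow six of the eight cohorts (1A to 1C and 2A to 2C). With three doses, at most 3 − 1 = 2 escalations can occur. These counts locate the decisions; they do not measure risk.

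**The case against.** The strongest reply is that 7.1.1 is not the only safety language. The synopsis and 2.2.1 require the dose to be judged safe as well as no halting rule to be met. Protocol 4.1 and SAP 4.1 say that the first cohort is there to show the virus is safe, without related or unanticipated AEs, before further use. Section 4.3 is still in force, since silence in 9.5.6.2 does not repeal it. This stands to the extent that a reader might infer that escalation rests on 7.1.1 alone, and the documents do not support that. But the general wording does not say that a severe complication makes a dose unsafe, and it allows a pause without requiring one. The first-cohort statement covers only that cohort.

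Other safeguards also narrow the gap. A severe complication leads to unblinding of staff and subject (4.1), so it would not pass unseen. The ISRC includes both site PIs, the medical monitor and the medical officer (10.1.6), and a PI can invoke item 5. Section 8.3.2.3 treats the study product as always suspect, so relatedness will seldom exclude an event. Discharge requires no moderate or severe influenza signs and 48 hours of stability (8.1.2), so a complication evident on Day 8 keeps the subject in confinement. The post-discharge gap is new onset after clearance.

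Three further inferences are tempting and not supported:

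- That only ICU cases count under item 3. ICU care is an included example; any related SAE in confinement qualifies.
- That the SAP expects non-serious severe complications because it lists them apart from SAEs: "Severe influenza complications reported as adverse events will be reported in" Table 62, with SAEs in Table 61. An SAE is also an AE, so one event may appear in both tables.
- That a met criterion would bar the higher dose for good. It pauses enrollment and dosing for SMC review.

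**Conclusion.** The plan is wrong as written, with moderate confidence. Section 4.1 misdescribes 7.1.1, and the separate condition in 4.3 is missing from the sections that state the operating rule.

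The practical reach is small: one related severe complication judged non-serious, or one that first arises after discharge and before the dose decision. For that case the plan permits a pause through several discretionary routes but does not require one. No rate is given for these events and the protocol expects them to be unlikely, so no probability is attached.

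The conclusion assumes that the halting criteria in 9.5.6.2 are those of 7.1.1. Section 9.5.6.2 does not cite 7.1.1, but 9.5.6.1 does. It also assumes that no unseen source closes the gap. Figure 1 may carry a safety condition, SOP CIVICs 001 may settle which listed complications count as serious, and the SMC charter may add a review.

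**What to change.** Add an item to 7.1.1: any severe influenza complication listed in 2.3.1, assessed as related to the challenge virus, in any challenged subject and known by the dose decision, pauses for SMC review. Have 1.1, 4.1, 4.3 and 9.5.6.2 refer to that item; SAP 4.1 follows through its citation of 7.1.1. The relatedness test matters because 2.3.1 also lists hospital admission and worsening of chronic conditions. Without it, an unrelated admission would pause the study. Check Figure 1, SOP CIVICs 001 and the SMC charter before settling the wording.

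If the narrower rule was intended, correct 1.1, 4.1 and 4.3 instead, so that they state the related-SAE and confinement limits.

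The change needs no extra subjects or procedures. The downside is a possible additional SMC pause for an event expected to be unlikely. Parts of the SAP describe the escalation decisions in the past tense; if dosing is complete, the CSR should state which rule governed them.
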